Any adverse events that are expected, not related to LEV, and not severe in nature will be recorded in the database, and reviewed at regular meetings of the DSMB. The DSMB will be able to review significant trends of adverse events at their meetings, since the DSMB will be the only party not blinded in this trial. After review of the data, the DSMB will report to the sponsor regarding the risks of the study and whether the risks are consistent with what is described in the informed consent form. These reports will be provided by the sponsor to the local IRBs for determining continuing review, and to the FDA for annual IND safety reports.

Any adverse events that are deemed by the investigator to be unexpected, possibly related to LEV, and severe in nature will be reported to the sponsor within 24 hours of the event. These unanticipated adverse events will also be reported by the PI to the local IRB in accordance with the local IRB policies. The sponsor will be responsible for reporting the unanticipated adverse events to the DSMB chair within 24 hours of receiving the report, and to the FDA in an IND safety report in accordance with FDA regulations. The DSMB will determine if the adverse event changes the known risk to study subjects. If the information changes the known risk to subjects, the DSMB's report regarding the change in risk will be released to all participating investigators by the sponsor. The DSMB may request changes to the DSMP.

Mechanisms to minimize potential risks to privacy and confidentiality of data

Privacy Provisions: The treating neonatology staff or pediatric neurologist will first approach a newborn's parents to ask permission for the study investigator to discuss the study with the family. Only if and after parents agree to this step will a study investigator then talk with the parents and review the subject's medical record. Once informed consent is obtained, the parents may need to answer a few questions about the maternal and family health history, but study staff will obtain most of the data from the subjects' medical records.

Confidentiality Provisions: The physicians and nurses caring for each newborn will need to know that the newborn is enrolled in this study but will not have access to data collected only for research purposes.

Medical information collected during this study will become part of the subject's hospital record, if the information is determined to be pertinent to the subject's medical care or is a usual part of the subject's care (e.g., results of tests ordered by treating clinicians that are also recorded for research purposes). Medical records are available to other health care professionals at the hospital and may be reviewed by hospital staff in their course of carrying out their responsibilities. However, they are required to maintain confidentiality in accordance with applicable laws and hospital policies. Information contained in a medical record may not be given to anyone unaffiliated with the hospital in a way that could identify the subject or parent without written consent, except as required or permitted by law. Information collected during the study that does not become part of a subject's medical record will be stored in separate research files maintained by the investigators. These research records will not be made available to any individuals who are not part of the research team except upon a parent's request or as required by law. If a subject is withdrawn from the research study, information that has already been collected will become part of the research database.

Only the research coordinator, neurology fellow and site PI at each NICU will have access to individually identifiable information about newborns enrolled at that site. Data will be collected by the study investigators and research coordinator and recorded onto case report forms (CRFs) by the research coordinator. The CRFs and the electronic database containing the research data will contain only de-identified information to preserve confidentiality of patients' protected health information. Only the study identification number will identify the subjects on the CRFs and in the electronic database. Files that link the study identification number for each subject to the subject's personal information (such as name, medical record number, parents' names) will be kept at each study site and accessible only by the site PI and research coordinator. The research database containing the subjects' study ID numbers and research data will be stored on a single computer, protected with a password, and will be backed up on the network in a private folder accessible only to study staff.

Mechanism to minimize potential risks of adverse drug reaction related to LEV

As described above LEV is a very safe drug with a wide therapeutic range. However, any adverse drug reaction is possible. Careful monitoring for adverse drug reactions will be maintained throughout the treatment period. Neonates will be monitored continuously during the study period for heart rate, respiratory rate and blood pressure. Serum chemistries and CBC will be performed at baseline and after 48 hours of treatment with study drug. Daily physical examinations will be performed while in-house and record made of the occurrence of hypotonia, sedation, poor feeding, irritability or infection. Since all subjects will be closely monitored by clinical, laboratory and EEG data, it is expected that adverse events can be anticipated and managed rapidly and effectively by the treating clinicians.

If there are serious adverse events, these events will be reported to the IRB within 24 hours of knowledge of the event, and will be reported to the DSMB in the timeframe that they require.

Mechanism proposed to minimize the patient's potential risks involving blood drawing

Blood drawing will be done by clinical staff who are trained and experienced in drawing blood from newborns. A clinically indicated indwelling arterial or venous catheter will be present in most study subjects, so that in most cases there will be no discomfort to the newborns from needle sticks for research-only blood draws. Sterile techniques will be used at all times to minimize the chance of infection, thereby minimizing potential risks related to the collection of blood samples. It is possible that in some subjects indwelling arterial or venous catheter access will not be maintained throughout the study period and may require additional venipunctures or heel stick blood draws. All efforts will be made to reduce infants discomfort by warming the heel adequately prior to blood draw, administering oral glucose during blood draw and feeding infant after blood draw.

Mechanism proposed to minimize patients' risk of time delay to effective AED therapy

Our study design ensures rapid escalation to treatment with Phenobarbital in subjects who do not respond to LEV. Additionally, because our study will utilize real time monitoring of continuous EEG recordings leading to more rapid detection and treatment of electrographic seizures than is normally standard of care, our study subjects will receive AED treatment in a shorter time frame than is usual. LEV has good efficacy in other

populations, including in populations experiencing refractory status epilepticus. In neonates there are accumulating reports of its efficacy in cases where seizures are refractory to multiple other agents. Our preliminary analysis of efficacy when LEV is used as a second line agent suggests efficacy similar to that of Phenobarbital and phenytoin when used as second line agents. Therefore we believe that the risk that the overall risk to patients is low in this regard

Specific Measures to reduce potential risks listed in (13)

1. Measures to reduce pain from venipunctures

For the first days of the study all patients will have indwelling vessel catheter in place as part of their routine care. This will render blood sampling painless and free of any risk beyond that usually associated with the care of a critically ill newborn. Blood sampling towards the end of the 1-week treatment period may require additional venipunctures or heel stick blood draws. All efforts will be made to reduce infants discomfort by warming the heel adequately prior to blood draw, administering oral glucose during blood draw and feeding infant after blood draw.

2. Measures to reduce risk secondary to blood loss from venipunctures

The total blood drawn over 2 days for the study will be 44 to 5 ml (4 x 0.5 ml specimens for levetiracetam levels, and at the same lab draw as the last levetiracetam level an additional 1.0 ml for chemistry CBC and phenobarbital level). By excluding infants with birth weights less than 2440g we will be able to ensure that this is a safe percentage ($\leq 3\%$) of the infants total blood volume.

3. Adverse drug reaction

As above levetiracetam is apparently a very safe drug with a wide therapeutic range. Adverse drug reactions to orally administered levetiracetam in adults and older children have been exceedingly rare. Use of the IV formulation in animal studies and a PK study in adults has so far not been associated with serious adverse drug reactions. However, any adverse drug reaction is possible including serious anaphylactic reaction and death. Careful monitoring for adverse drug reactions will be maintained throughout the treatment period:

Levetiracetam has been well tolerated in other age groups and found to be without significant risks. Adverse events have mainly consisted of CNS effects such as somnolence, asthenia, coordination difficulty and behavioral symptoms. Other than 2 cases of reversible thrombocytopenia associated with levetiracetam use, no unexpected toxicities or serious laboratory abnormalities have been reported.

Neonates will be monitored continuously during the study period for heart rate, respiratory rate and blood pressure.

Serum chemistries, and CBC will be performed at baseline and at end of treatment.

Daily physical examinations will be performed while in-house and record made of the occurrence of hypotonia, sedation, poor feeding, irritability or infection.

Following the last dose of study drug, a phone review of the same symptoms will be conducted every 3 days and a visit and physical examination will be conducted one week after the last dose of study drug. A home visit or clinic visit can be conducted if the subject is discharged.

4. Mechanism proposed to minimize patients' risk of time delay to effective AED therapy

Our study design ensures rapid escalation to treatment with Phenobarbital in subjects who do not respond to LEV. Additionally, because our study will utilize real time monitoring of continuous EEG recordings leading to more rapid detection and treatment of electrographic seizures than is normally standard of care, our study

subjects will receive AED treatment in a shorter time frame than is usual. LEV has good efficacy in other populations, including in populations experiencing refractory status epilepticus. In neonates there are accumulating reports of its efficacy in cases where seizures are refractory to multiple other agents. Our preliminary analysis of efficacy when LEV is used as a second line agent suggests efficacy similar to that of Phenobarbital and phenytoin when used as second line agents. Therefore we believe that the overall risk to patients is lower than the usual clinical care risk when using our treatment protocol. The continuous EEG monitoring that will be used for the study will mean that these determinations of the efficacy of medications will be possible sooner than is possible with routine management.

5. Measures to safeguard confidentiality of data.

Personal identifiers such as name, date of birth and medical record number will be eliminated from each case as it is entered in the database. A single copy of the list linking medical record number to study number will be kept locked and will be available only to study investigators. Data will be entered on single secure database, accessible only by study investigators. The code will be destroyed at the end of the study.

15. POTENTIAL BENEFITS:

The main benefit of the study will be to society and future neonates with seizures, in the knowledge that will be gained from the study. If LEV efficacy, safety and pharmacokinetics can be established in neonates this will be of great benefit to all neonates with seizures. Developing better infrastructures to increase the feasibility of continuous monitoring and the early detection of neonatal seizures will also significantly improve the management of this condition.

Several potential benefits to enrollment in this study compare favorably with the low risks associated with participation in the study. One principal benefit of this study is that early and more intensive “real time” EEG monitoring will likely lead to more rapid diagnosis and treatment of neonatal seizures than in the current standard of care. Subjects enrolled in both treatment and control groups will have the potential benefit of this early EEG monitoring.

Although there are potential risks associated with administration of LEV, the overall risk of adverse events are low. All subjects will be carefully monitored with respect to clinical, laboratory and EEG data in a more systematic fashion than is typical in the care of such newborns, thus any adverse event will be recognized quickly. Our study design ensures rapid escalation to standard treatment with Phenobarbital in subjects who do not respond to LEV. Additionally, because our study will utilize real time monitoring of continuous EEG recordings leading to more rapid detection and treatment of electrographic seizures than is normally standard of care, it is likely our study subjects will receive AED treatment in a shorter time frame than is usual.

Benefits to the individual participant:

Potential Benefits of the Proposed Research to Human Subjects and Others

There may be no benefit to the individual participant. A potential benefit of this study is that earlier placement of EEG leads and greater than routine monitoring of the prolonged EEG recording, clinical and laboratory data will improve the overall management of the subjects’ seizures and other clinical conditions, compared with standard management of these patients. In particular, there will likely be more rapid diagnosis and management of seizures than in the standard care of newborns with seizures, because of the early, continuous EEG monitoring analyzed in near-real time. This relates in part to the lack of availability of rapid placement of EEG electrodes and less vigilant or less frequent/prolonged monitoring of EEG data for recurrent seizures in the standard clinical care of newborns. EEG monitors cannot usually be placed rapidly because of the lack of available EEG technologists to place EEG leads on an urgent basis, especially at night or on weekends. In standard practice, continuous EEG monitoring is often not started until seizures are

clearly shown to be refractory, which may not be recognized when most or all of the seizures are electrographic only (subclinical). EEG monitoring for clinical purposes is often intermittent rather than continuous and prolonged over two days.

Another potential benefit of the study to the participant is that LEV may be a more effective antiepileptic medication than the standard treatments. It is also a potential benefit to the participant that LEV may be a safer drug associated with fewer side effects than the standard treatments.

Benefits to society:

Importance of the Knowledge to be gained

There are no FDA approved treatments for neonatal seizures. More effective and less toxic treatments are urgently required. Neonatal seizures are a common problem and cause significant morbidity. Current standard of care treatments Phenobarbital and phenytoin are unsatisfactory¹, each agent is effective in less than 50% of subjects, and both have significant acute and chronic side effects. In animal studies these agents cause accelerated neuronal apoptosis in the neonatal brain. Better treatments could limit brain damage and improve neurodevelopmental outcomes in this high risk population. LEV has great potential as a treatment for neonatal, however; the efficacy of LEV has not been systematically studied in neonates and cannot be assumed. Drugs that are effective in terminating seizures in adults may be less effective and have more toxicity in neonates.

Efforts to develop better treatments for neonatal seizures are confounded by the need in any drug trial for systematic continuous EEG monitoring, something that is not yet standard of care because of resource constraints. The proposed project would address the need to find feasible solutions to the difficulties of providing continuous EEG monitoring through new technology.

Should LEV prove an effective medication in this age group, clinical practice would be dramatically improved. We would have a safe, non-toxic treatment option for neonatal seizures with proven efficacy.

Developing better systems for neonatal seizure detection will facilitate earlier treatment of neonatal seizures and enable further clinical research in this condition.

If levetiracetam efficacy, pharmacokinetics and safety can be established in neonates with seizures this will be of great benefit to all neonates with seizures.

This study will be registered in ClinicalTrials.gov. website as required by the FDA.

16. RISK/BENEFIT RATIO:

No drug study in neonates is without risk, however IV levetiracetam appears to be a very safe drug. There is a dire need for better anti-epileptic agents for neonates and there are substantial risks associated with the use of standard therapies. The potential benefit to all neonates with seizures outweighs the risks that would be involved in this study. There is considerable potential that the risk/benefit ratio is favorable in the study subjects themselves.

17. EXPENSE TO SUBJECT:

None.

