40% develop cerebral palsy and/or mental retardation⁶. The most recent prospective long term follow-up of clinical neonatal seizures in the province of Newfoundland reported on all live newborns born between 1990 and 1995. Data was available on 82 of 90 children. In 28 term babies only 45% were normal, 16% died, and 32% were impaired⁶. Whilst much of the mortality and morbidity in neonates with seizures can be attributed to the underlying condition, there is mounting evidence that seizures themselves are harmful, especially in the asphyxiated neonatal brain. Studies in rats show that seizures can damage the developing brain^{7, 8}. McBride et al have demonstrated a strong correlation between the amount of electrographic seizure activity and subsequent morbidity and mortality⁹. Preliminary data also demonstrates an improved outcome with prompt and complete cessation of seizures⁴ and in a recent European controlled trial, treatment of subclinical seizures showed a trend for reduction in seizure duration which was associated with less brain injury on MRI¹⁰. Brain MR spectroscopy in neonates suffering seizures secondary to perinatal asphyxia shows brain injury as a consequence of the seizures¹¹. Recent evidence suggests that neonatal seizures independently contribute to poor outcome at 4 years of age in neonatal hypoxic-ischemic injury¹².

Current AEDs for Neonatal Seizures:

Current treatment relies on medications in use since 1914 (Phenobarbital) and 1938 (phenytoin). These agents are neither effective nor safe. Treatment with Phenobarbital or phenytoin produces cessation of neonatal seizures in less than 50% of infants treated¹. Acute side effects of phenobarbital and phenytoin include hypotension, suppression of respiratory drive, cardiac arrhythmia and sedation. Chronic exposure to phenobarbital may be associated with decreased cognitive ability¹³⁻¹⁵.

Neonatal response to AEDs is different to that of adults:

The neonatal response to AEDs is fundamentally different to that of the adult brain^{5, 16, 17}. Neonatal seizures form a unique subset of pediatric seizures for a number of reasons:

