Subjects randomised to receive LEV will, at the onset of electrographically confirmed seizure activity, receive an intravenous loading dose of LEV of 40mg/kg given over 15 minutes. If electrographic seizures are confirmed to persist or recur more than 15 minutes after the first infusion is complete, a further 20mg/kg load of LEV will be administered IV over 15 minutes. Maintenance LEV at 10 mg/kg/dose will be given IV q8 hours and continued for at least 5 days. If seizures persist or recur more than 15 minutes after the second LEV infusion is complete, a PB loading dose of 20 mg/kg will be administered IV over 15 minutes. If seizures persist or recur more than 15 minutes after the first loading dose of PB is complete, a second 20mg/kg load will be administered IV over 15 minutes. This will result in PB being started within 1 hour of the onset of seizures if and when loading with LEV is ineffective. Patients given any PB loading doses will be started on maintenance PB with 1.5 mg/kg/dose given IV q8 hours and continued at least until the end of the study

Figure 2 details the study flow.

Subjects randomized to the control group will, at the onset of electrographically confirmed seizure activity, receive an intravenous loading dose of PB of 20 mg/kg given over 15 minutes. If electrographic seizures are confirmed to persist or recur more than 15 minutes after the first infusion is complete, a further 20mg/kg load of PB will be administered IV over 15 minutes. Maintenance PB at 1.5 mg/kg/dose will be given IV q8 hours and continued for at least 5 days. If seizures persist or recur more than 15 minutes following the second PB infusion, a 40 mg/kg load of LEV will be administered IV over 15 minutes. If seizures persist or recur more than 15 minutes after the first loading dose of LEV is complete, a second 20mg/kg load of LEV will be administered IV over 15 minutes. Patients given an LEV loading doses will be started on maintenance LEV with 10 mg/kg/dose given IV q8 hours and continued at least until the end of the study.

If electrographic seizures are still apparent following treatment with both LEV and PB, or if they recur during the 5 days during which the study protocol is active, the patient will be considered to have failed the experimental treatment regime and institutional specific standard seizure management will dictate the ongoing

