Feasibility data: We will record the times of the following events: subject admission to NICU, contact of study staff by treating physicians, subject enrolment, initiation of EEG monitoring, first recognized seizure, and time of study drug administration. Record will be made of whether seizure is first identified by Corticare staff or by onsite study investigator. Record will be systematically collected from each monitored subject of any difficulties with functioning of the remote continuous monitoring infrastructure. All data will be referenced to date/time of birth so that precise age in hours can be determined for age at enrolment, timing of seizures, administration of study drug, and administration of other treatments given to treat seizures.

Safety data: Continuous monitoring of vital signs will occur as part of routine neonatal intensive care. Vital signs will be recorded at baseline, and at 15 minutes after each drug infusion commences. Documentation of presence or absence of adverse event occurring during each treatment phase will be made. Blood tests of haematological indices, electrolytes, glucose, renal function and liver enzymes will be tested and recorded at baseline, at 24 hours and at 48 hours as part of safety and adverse events monitoring.

Pharmacokinetic data: For subjects at the 3 San Diego sites serum LEV levels will be drawn at baseline, 1 hour after starting the treatment, at 24 and 48 hours.

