## 7.5 Analysis of Safety Outcomes

Adverse Event and Serious Adverse Events will be tabulated by randomization group and by drugs received, respectively. Details including seriousness, intensity, causality, withdrawal due to event and outcome will be summarized by frequencies and percentages by randomization group and by drugs received. Fisher's exact tests will be used to compare rates of adverse events, serious adverse events, study discontinuation and deaths between randomization group and by drugs received, respectively.

Findings will be tabulated by randomization group overall and for findings marked as AE and SAE, respectively.

Safety Labs (using DAIDS guidelines) will be presented with shift tables (hour 48 vs baseline) by randomization group and by drugs received, respectively.

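### The daily prompted harm list omits three of the four acute harms that the protocol names for phenobarbital, and the SAP names no cardiorespiratory safety outcome, so the LEV versus PB safety comparison may miss such harm

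*Protocol*

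**What the plan says.** Protocol section 14, in the part on minimizing adverse drug reactions to LEV, requires a daily examination with "record made of the occurrence of hypotonia, sedation, poor feeding, irritability or infection". The same list appears under Specific Measures, item 3. After the last dose, "a phone review of the same symptoms will be conducted every 3 days". That item describes the LEV experience in other age groups as follows: "Adverse events have mainly consisted of CNS effects such as somnolence, asthenia, coordination difficulty and behavioral symptoms".

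For the control drug, Protocol section 6 (Current AEDs for Neonatal Seizures) states: "Acute side effects of phenobarbital and phenytoin include hypotension, suppression of respiratory drive, cardiac arrhythmia and sedation".

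Protocol section 8 (Safety data) sets the only timed vital-sign record: "Vital signs will be recorded at baseline, and at 15 minutes after each drug infusion commences". It also asks for a yes/no on adverse events in each treatment phase. Heart rate, respiratory rate and blood pressure are monitored continuously as part of care. Section 9 lists blood pressure and administered medications among the trial data, without a schedule.

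SAP 4.4 lists as safety outcomes the AE rate, SAE rate, discontinuation rate, laboratory data and PK. In SAP 7.5, "Fisher's exact tests will be used to compare rates of adverse events", and likewise SAEs, discontinuation and deaths, by randomized group and by drugs received.

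**The concern.** A harm that is asked about by name every day is usually recorded more completely than one that someone must notice, judge to be an adverse event and write down. In this population the second route is fragile. Section 14 treats any event associated with systemic asphyxia or HIE as expected, and section 9 describes infants who already have respiratory and cardiac complications. A fall in blood pressure or a need for more respiratory support is easily put down to the underlying illness.

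The general considerations in section 8 say that the two groups will be compared on safety, the Aim 4 analysis does so with Fisher's exact test, and section 15 raises the possibility that LEV is the safer drug. Cardiorespiratory harm is where the protocol's own account of phenobarbital would lead one to look for a difference, yet it has neither a prompted item nor a named outcome.

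**Working it through.** The plan states no adverse event rate, safety power or capture rate, so there is no safety figure to reproduce. The check is mainly a matching of harms to recording rules.

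**1. Coverage.** Acute harms named for phenobarbital (with phenytoin) in section 6, against the daily list in section 14:

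| Harm | On daily list? | Other routes into the data |
|---|---|---|
| Sedation | Yes | Per-phase AE yes/no |
| Hypotension | No | Per-infusion vital signs; unscheduled blood pressure data; per-phase AE yes/no |
| Respiratory depression | No | Per-infusion vital signs; per-phase AE yes/no |
| Arrhythmia | No | Per-infusion vital signs; per-phase AE yes/no |

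On the list: 1 of 4. Off it: 3 of 4 = 75%.

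**2. Timing.** Control infants "receive an intravenous loading dose of PB of 20 mg/kg given over 15 minutes", and LEV loads run for the same time. A record 15 minutes from the start therefore falls 15 − 15 = 0 minutes after a load ends, so it cannot show an effect that appears later.

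**3. Frequency.** This turns on what counts as an infusion.
- Loads only: an infant receives 1 to 4 loads, giving 1 to 4 records after baseline. An infant who responds to the first load has one.
- Maintenance included: "Maintenance PB at 1.5 mg/kg/dose will be given IV q8 hours and continued for at least 5 days", and LEV maintenance has the same interval. That gives 24/8 = 3 records a day, or 3 × 5 = 15 over five days for one drug, which is more often than the daily examination.

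The protocol does not say which is meant.

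**4. Conversion to an outcome.** No passage says when a monitored or recorded vital sign becomes an adverse event. SAP 4.4 and 7.5 contain no analysis of vital signs, hypotension, arrhythmia or respiratory support.

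**5. What incomplete capture does (all rates assumed).** Let c be the fraction of a given harm that is recorded, equal in both arms. The recorded difference is c × (p_PB − p_LEV). With 30% against 10% and c = 0.5, this is 0.5 × 0.20 = 0.10. Power is the exact power of a two-sided Fisher test at 0.05 with 40 PB and 60 LEV infants. As a check of the method, the same calculation for the plan's efficacy case (50% against 22%) gives 79.6%, against the stated 80%.

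| True PB vs LEV | c = 1 | c = 0.75 | c = 0.5 | c = 0.25 |
|---|---|---|---|---|
| 30% vs 10% | 66.9% | 50.3% | 32.4% | 14.5% |
| 40% vs 10% | 93.2% | 80.5% | 57.7% | 28.3% |
| 20% vs 5% | 57.7% | 43.7% | 28.3% | 8.3% |

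**6. Direction.** For one type of harm, equal under-capture shrinks the difference but does not reverse it. Over all types k, the difference in expected recorded events per infant is the sum of c_k × (p_PB,k − p_LEV,k). Prompted types then count for more than unprompted ones, so the total can be skewed. The sign depends on every p and c, and the documents give none of them.

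**The case against.** The case on the other side is substantial. The same list is applied in both arms under blinding by equal-volume loads. The AE yes/no per treatment phase is an active record of any kind of event. Section 14 sends expected, non-severe events unrelated to LEV to the database. Section 9 makes blood pressure and medications trial data, and SAP 7.5 tabulates findings as well as AEs. Infants can cross over to the other drug after two loads, which dilutes any contrast by randomized arm. The case report forms are not among the documents and may prompt for more than section 14 does.

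Two stronger readings are tempting, and these points defeat both.

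- A reader might infer that phenobarbital's acute harms are recorded only once per infusion and otherwise reach the database only if volunteered. That schedule describes the vital-sign record, not AE recording, and if maintenance counts it is more frequent than daily.
- A reader might infer a demonstrated tilt against LEV, and try to size it by setting the share of pilot events on the daily list (2 sedation + 3 feeding = 5 of 8) against the 1 of 4 phenobarbital harms on it. This compares a share of events with a share of harm types. The protocol judged the feeding problems probably not due to LEV, and every pilot infant had already received phenobarbital. Two of the eight events (apnea with bradycardia, and an intubation) were cardiorespiratory and off the list, so the omission also affects events seen under LEV. Sedation, which is on the list, is itself a named phenobarbital harm, and infection is neither a sedation nor a behavior effect.

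What remains is that the general routes carry no named cardiorespiratory item, no threshold and, for blood pressure, no schedule, and that nothing in the SAP draws on them as an outcome.

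**Conclusion.** The point holds as a gap in ascertainment and in outcome definition, not as a demonstrated bias. Three of the four acute harms named for phenobarbital have no prompted daily item, no recording threshold in the documents and no outcome in the SAP, although the plan compares the two drugs on safety. Uneven prompting could under-capture these events, weaken the comparison and possibly skew it.

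Neither size nor direction can be derived from the documents. The loss of power shown above (for example 67% to 32% when half of events are captured) rests wholly on assumed true rates and on equal capture in both arms, and it ignores crossover. The point also assumes that the case report forms add no prompts beyond those in section 14. It merits action because the remedy is cheap.

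**What to change.** - **Collection.** In both places in Protocol section 14 where the daily list appears, add hypotension, respiratory depression (including apnea or increased respiratory support) and bradycardia or arrhythmia as prompted items. Write the recording definitions in advance. They should say what is to be recorded and should not act as triggers for care. Apply them identically and blinded in both arms, using the monitoring already in place.
- **If recruitment has closed.** Section 11 refers to a review after recruitment closure, so new daily items may come too late. The same items can then be extracted from charts by staff blinded to allocation, with definitions fixed before unblinding. This must precede destruction of the linking code, which section 14 places at the end of the study and section 29 at publication.
- **SAP.** Name the three harms as safety outcomes in 4.4, and compare them in 7.5 alongside the overall AE rates, by randomized group and by drugs received as for the other safety outcomes.
- **Clarification.** State in section 8 (Safety data) whether the per-infusion vital-sign record includes maintenance doses.

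The cost is three added items per day, or a limited chart review, together with a short SAP amendment. More background events will be recorded in both arms.
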